#### 4.6 Mortality, Hospitalization[EVENT3 and AE2] (ITT)

- a. Number (%) dying showing whether or not the death occurred on or before 28 days versus greater than 28 days from randomization.

- b. List of deaths: Randomized arm, days from randomization to death, subject ID, age, sex, site, confirmed influenza infection status, days from the last dose of study treatment taken to death, primary cause of death, relatedness to study intervention. List to include all deaths reported, irrespective of time from randomization to the date of death (i.e. including any deaths reported after 28 days). Sort by randomized arm, days from randomization to death and subject ID.
- c. Figure and Analysis: Kaplan-Meier plot of time from randomization to death (censoring at Day 28 visit date if completed, or at date of last contact if lost to follow-up prior to Day 28 visit), with associated table showing: number censored and number (%) dying; p-value from log-rank test.
- d. The percentage of subjects dying by 28 days will be estimated from the Kaplan-Meier curves and Greenwood's formula for the standard error of this estimate will be used to construct 95% confidence intervals for the mortality rates and the difference between treatments in the mortality rates.
- e. If the number of hospitalizations is small in one randomized arm, an alternative confidence interval will be constructed by inverting an exact binomial test of the actual percentages (but ignoring loss to follow-up).
- f. Analyses of time to hospitalization and the derivation of 28-days percentage of subjects being hospitalized will be analyzed in a similar manner to that for time to death.

## 4.7 Safety Analysis

### 4.7.1 Serious Adverse Events (Enrolled population and ITT)

- a. Enrolled Population: Number (%) of subjects with an SAE by MedDRA System Organ Class (SOC) and Preferred Term (PT); number (%) of subjects with any SAE. This table will include all SAEs, irrespective of time from randomization to the date of onset of the SAE (i.e. including any SAEs reported before randomization or after 28 days).
  - Table repeated to show total number of SAEs (i.e. allowing a subject to be represented more than once per row, SOC header, and in total numbers).
  - ITT Population: Number (%) of subjects with an SAE by MedDRA System Organ Class (SOC) and Preferred Term (PT); number (%) of subjects with any SAE through to the date of the Day 28 visit (or death on/before 28 days).
  - Table repeated to show total number of SAEs (i.e. allowing a subject to be represented more than once per row, SOC header, and in total numbers).
- b. Enrolled Population: List of SAEs: Randomized arm, days from randomization to first SAE experienced by a subject, subject ID, site, confirmed influenza infection status, days from randomization to the date of the SAE, days from first and from last dose of study treatment to the date of SAE, SAE (MedDRA SOC and PT, and verbatim description), severity grade, relatedness to study intervention, outcome (e.g. died/resolved/ongoing) (sort by randomized arm, days from randomization to first SAE, subject ID, and, if a subject has multiple SAEs, days from randomization to SAE).

#### 4.7.2 Adverse Events (Enrolled population, and ITT)

- a. Enrolled Population: Number (%) of subjects with an AE (as defined above) by MedDRA System Organ Class (SOC) and Preferred Term (PT); number (%) of subjects with all AEs irrespective of time since randomization (i.e. including any reported before randomization or after Day 28).
  - Table repeated to show total number of AEs (i.e. allowing a subject to be represented more than once per row, SOC header, and in total numbers).
- b. ITT Population: Number (%) of subjects with an AE (as defined above) by MedDRA System Organ Class (SOC) and Preferred Term (PT); number (%) of subjects with all AEs from Day 0 to Day 28.
  - Table repeated to show total number of AEs (i.e. allowing a subject to be represented more than once per row, SOC header, and in total numbers).
- c. ITT Population: Number (%) of subjects with an AE (as defined above) by MedDRA System Organ Class (SOC) and Preferred Term (PT); number (%) of subjects with all related AEs (definitely related, probably related, possibly related) from Day 0 to Day 28.
  - Table repeated to show total number of AEs (i.e. allowing a subject to be represented more than once per row, SOC header, and in total numbers).
- d. Enrolled Population: List of AEs: Randomized arm, days from randomization to first AE experienced by a subject, subject ID, site, confirmed influenza infection status, days from randomization to AE, days from last dose of study treatment, AE (MedDRA SOC and PT, and verbatim description), severity grade, relatedness to study intervention, outcome, e.g., died/resolved/ongoing, sorted by randomized arm, days from randomization to first AE, subject ID, and, if a subject has multiple AEs, days from randomization to AE.

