6 STUDY PROCEDURES

The following table (Table 4) outlines all of the assessments to be conducted during the study. A detailed presentation of assessments immediately follows the table. Total volumes of blood drawn are noted in the text for each study day. Details regarding the research samples (tubes, swabs, etc) will be detailed in the Manual of Procedures. The day when the subject is enrolled and randomized is denoted as Study Day 0, the first day after randomization is Study Day 1, etc.

Table 4: Schedule of Assessments

| Day +/- Window Evaluation/Procedure | Screen | Baseline | | | | | |
|--|---------------|-----------------|--------|--------|---|-------|--------|
| | -1 to 0 | 0 | 1 Home | 2 Home | 3 | 7 ± 1 | 28 ± 3 |
| ELIGIBILITY | | | | | | | |
| Informed consent | X | | | | | | |
| Demographics | X | | | | | | |
| Medical history | X | | | | | | |
| Site influenza testing (PCR or rapid Ag, See Section 7.2.2) | X | | | | | | |
| RANDOMIZATION/ STUDY DRUG | | | | | | | |
| Randomize subject | | X | | | | | |
| Dispense Study Treatment Kit | | X | | | | | |
| STUDY PROCEDURES | | | | | | | |
| Review and collect diary card (see Section 7.3.1) | | X ¹ | | | X | X | X |
| Assess for complications of influenza (see Section 7.3.2) | | X | | | X | X | X |
| Vital signs, including SaO ₂ (see Section 7.3.3) | X | X | | | X | X | X |
| Assessment of study drug compliance (see Section 7.5) | | | | | X | | |
| Review of concomitant medications | | | | | X | X | X |
| Physical exam ² (see Section 7.1.2) | X | | | | X | X | X |
| Adverse events | | | | | X | X | X |
| SAFETY LABORATORY | | | | | | | |
| Urine βHCG (for females of childbearing potential) | X | | | | | | |
| REFERENCE PROCEDURE | | | | | | | |
| Nasopharyngeal swab for virus isolation | | X | | | X | X | |
| Subject sample self-collection (see Section 6.3.3.2) | | X | X | X | X | | |
| Stored Serum | | X | | | X | X | X |

Notes: 1. On Day 0, subject will be instructed on how to complete the diary card, and baseline assessment will be collected.

2. Brief physical examinations will be conducted at screening to ensure there are not medical conditions (either chronic or acute) that would increase a subject's risk for participation in this study. Symptom-targeted physical examinations will be conducted at all other visits as needed to evaluate new complaints and possible adverse events.

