6.3 Detailed Description of Assessments

6.3.1 Study Day –1 to 0: Screening

Screening is defined as the period of evaluation after signing the informed consent that is used to determine if a subject is eligible for randomization. Up to 24 hours is permitted between enrollment (signing consent) and the first dose of study medication. However, efforts should be made to minimize the time between enrollment and the first dose of study to the extent possible.

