6.3.3 Study Day 0: Baseline Evaluation

Baseline evaluation must be completed prior to the first dose of study medication.

6.3.3.1 Clinical Data on Day 0

- Assessment for presence of complications of influenza (See Section 7.3.2)
- Vital signs, including SaO₂ and height (See section 7.3.3)
 - If this assessment is within 6 hours from the screening assessment, the screening vitals can be used, otherwise vital sign measurements should be repeated for this assessment
- Assessment for AEs occurring after consent and prior to administration of study drug

6.3.3.2 Research Procedures on Day 0

At baseline, the following research procedures will be performed:

- Nasopharyngeal (NP) swab

All subjects will also be instructed on self-collection of nasal swabs. The subject should perform the first self-collection at this time in the research facility/ clinic with the study staff present. The self-collection procedure can be found in the Manual of Operations (MOP) and will be described in written instructions that may be provided to the subject.

See Section 7.3.4 for an overview of the planned virology assessments.

6.3.3.3 Reference Laboratory Tests on Day 0

- Up to 20 mL of blood will be taken for the stored samples (see section 7.4)

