6.3.3.4 Study Day 0: Study Drug Distribution

The study drug kit will be distributed to the subject, with instruction on how to take each dose every 12 hours. Treatment should begin as soon as possible. However up to 24 hours is permitted between enrollment (signing consent) and the first dose of study medication. To ensure timely administration of the first dose of the study medication, it may be taken in the research facility/ clinic. The time that the first dose is taken should be recorded.

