9.1 General Considerations

All statistical inferences will be based on two-sided tests with an α -level of 0.05. Categorical data will be summarized by the number and percent of subjects falling within each category. Continuous variables will be summarized by descriptive statistics, including mean, standard deviation, minimum, maximum, median, and relevant percentiles. Time-to-event endpoints will be summarized by median durations, hazard ratios, and corresponding 95% confidence intervals. Study Day 0 will be defined as the day of randomization.

The Statistical Analysis Plan will provide the procedure for accounting for missing, unused, and spurious data.

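### The ITT safety tables use different windows for AEs and SAEs and no first-dose start; the effect is small, but one common interval should be stated

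*SAP*

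**What the plan says.** **AE tables.** SAP 4.7.2 item b gives, for the ITT population, "number (%) of subjects with all AEs from Day 0 to Day 28". Item c gives "number (%) of subjects with all related AEs (definitely related, probably related, possibly related) from Day 0 to Day 28".

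**SAE table.** For the same population, SAP 4.7.1 gives "number (%) of subjects with any SAE through to the date of the Day 28 visit (or death on/before 28 days". It states no start date, and no end date for a survivor who never attends that visit.

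**Day count.** Protocol 9.1: "Study Day 0 will be defined as the day of randomization". Protocol 6 counts on from there: "the first day after randomization is Study Day 1, etc".

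**Dosing and event collection.** Protocol 6.3.1: "Up to 24 hours is permitted between enrollment (signing consent) and the first dose of study medication". Protocol 8.3.2 records AEs from signed consent through Day 28. The Day 0 procedures in Protocol 6.3.3.1 include "Assessment for AEs occurring after consent and prior to administration of study drug". Protocol 6.3.3.4 adds: "The time that the first dose is taken should be recorded". SAP 4.3.3 item c uses that time (source SDCOMP1) to summarize hours from randomization to treatment start.

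**Visit window.** SAP Table 1 gives the Day 28 visit as 28±3 per protocol and 28±7 for analysis.

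**Population and display.** SAP 4.1 defines ITT as randomized subjects with at least one dose. SAP 4 shows tables by randomized arm unless stated otherwise.

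**The concern.** The ITT definition selects subjects who were dosed. It does not select events that followed dosing, and SAP 4.7 has no treatment-emergent rule. The time-restricted by-arm tables can therefore include events that study drug could not have caused.

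Protocol 8.2 defines an SAE as a kind of AE. A reader will expect every SAE in the ITT SAE table to appear in the ITT AE table as well. With two sets of limits that need not be so, and the mismatch would have to be explained after unblinding.

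The listings cure only part of this. The SAE listing carries days from first dose. The AE listing carries days from randomization and from last dose only, so an AE that preceded dosing cannot be picked out directly.

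**Working it through.** The plan states no figure to reproduce, so the check sets the windows side by side, in study days from randomization.

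**1. Literal windows**

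| ITT table | Start | End |
|---|---|---|
| AE, related AE | Day 0 | Day 28 |
| SAE | not stated | date of Day 28 visit, or death on or before 28 days |

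Days 0 to 28 are 29 days.

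**2. Start.** At most 24 hours separate consent from first dose. Pre-dose time inside the AE window is therefore at most about 1 of 29 days: 1/29 = 3.4%. It is less when part of the 24 hours falls on Day −1, which the AE window already excludes. The SAE wording has no lower limit, so a Day −1 SAE in a subject later randomized and dosed fits the SAE table but not the AE table.

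**3. End.** The SAE window is taken from Day 0 here.

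| Day 28 visit held on | Days in SAE table only | Days in AE table only | Share of the longer window |
|---|---|---|---|
| Day 25 (protocol limit) | none | 26–28 | 3/29 = 10.3% |
| Day 28 | none | none | 0 |
| Day 31 (protocol limit) | 29–31 | none | 3/32 = 9.4% |
| Day 21 (analysis limit) | none | 22–28 | 7/29 = 24.1% |
| Day 35 (analysis limit) | 29–35 | none | 7/36 = 19.4% |

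**4. How many SAEs.** The documents give no SAE rate. Assume a 28-day risk r of 0.5% to 2%, constant hazard, and all 560 subjects seen d days late, which is an upper bound. Expected SAEs in SAE-only days = 560 × r × d/29.

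- d = 3: 560 × 0.005 × 3/29 = 0.3, up to 560 × 0.02 × 3/29 = 1.2.
- d = 7: 560 × 0.005 × 7/29 = 0.7, up to 560 × 0.02 × 7/29 = 2.7.

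**5. Effect of pre-dose events on the arm comparison.** Let the comparator have 1 unit of tabulated events, a share f of them pre-dose. Let the other arm have the same pre-dose count and twice the post-dose count.

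- Tabulated: 1 and f + 2(1 − f) = 2 − f. The difference is 1 − f and the ratio is 2 − f.
- Post-dose only: 1 − f and 2(1 − f). The difference is again 1 − f and the ratio is 2.

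The difference in event counts is unchanged. Only a ratio shrinks: with f = 1/29, from 2.00 to 1.97. In tables that count each subject once, let p be the pre-dose risk, independent of later events, and q1 and q0 the post-dose risks. The risk in each arm is p + (1 − p)q, so the difference is (1 − p)(q1 − q0). It shrinks only by the factor 1 − p.

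**The case against.** **The end mismatch depends on one reading.** SAP Table 1 has a visit named Day 28, and Protocol 3.2 identifies the final follow-up visit with Study Day 28. If Day 28 in SAP 4.7.2 is that visit label, the two windows end together and the late-SAE example disappears. This stands as a possible reading. However, SAP 4.6 treats 28 days from randomization and the Day 28 visit date as separate things, so the text does not settle it. The start mismatch and the missing end for survivors without a visit remain either way.

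**Little would be recorded before dosing.** Protocol 8.3.1 leaves out Grade 1–3 influenza symptoms and known oseltamivir effects. Conditions present at consent go to medical history (Protocol 6.3.1.3), hospitalized subjects are excluded at enrollment, and the first dose may be taken in the clinic. The related-AE table screens further, because causality usually implies a relationship in time (Protocol 8.3.5). All of this stands and limits the size.

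**Two stronger inferences are tempting.**

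- A reader might infer that pre-dose events bias the safety comparison toward no difference. The documents do not support that. Under blinded 1:1 randomization these events should be balanced, the difference in event counts is unchanged, and SAP 4.7 plans no ratio, test or confidence interval. Nothing in the documents supports a pre-dose share as high as 10% or 20%.
- A reader might infer that these are the only comparative safety tables. They are not. The Enrolled Population tables are also by arm under the SAP 4 default and have no time limit. Death, hospitalization and complications are compared formally in SAP 4.6 and 4.9.

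**Starting at randomization is a defensible convention.** That is fair, but the SAE table does not state it either, so the tables still disagree.

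**Conclusion.** The windows in SAP 4.7 are inconsistent as written. Pre-dose events can be tabulated under an arm. An SAE can be in the ITT SAE table and absent from the ITT AE table, or the reverse after an early visit. The SAE cut-off is undefined for a surviving subject without a Day 28 visit.

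The consequence is minor: noise from at most about 3.4% of the AE window, and probably no more than one or two irreconcilable SAEs within the protocol visit window (0.3 to 1.2 expected at the assumed upper bound). It is not directional bias, and no event is lost from the Enrolled Population tables.

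The end mismatch rests on reading Day 28 as a calendar day; the start problem does not. The SAE counts rest on assumed risks. The SAP's introduction and list of key updates were not available, so a safety window stated only there would change this conclusion.

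**What to change.** In SAP 4.7.1 and 4.7.2, state one interval and apply it to every ITT AE, related-AE and SAE table:

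- **Start:** first dose, from the time already held in SDCOMP1.
- **End:** one stated date consistent with Protocol 8.3.2, or death or last contact if earlier. Say explicitly whether Day 28 means the calendar day or the visit date.
- **Dosing-day events:** a date filter cannot separate these. Classify by onset time where recorded, otherwise by whether the event was reported at the Day 0 pre-dose AE assessment. If still unresolved, count the event as post-dose.
- **Listing:** add days from first dose to the AE listing, as the SAE listing already has.
- **Pre-dose events:** keep them in the Enrolled Population tables and listings.

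The cost is SAP wording, a short classification rule and its programming, and slightly fewer events in the ITT tables. No new data collection is needed, because the fallback covers events without an onset time.

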#### 4.8 Efficacy Analysis

The following efficacy analyses will be presented for the Primary Efficacy Population (study participants with confirmed influenza) and also for the Intent to Treat Population. The primary analysis of the primary endpoint will exclude the 50 subjects enrolled in the pilot study. A secondary analysis will, however, be undertaken which includes these 50 subjects. All analyses of secondary efficacy endpoints will be undertaken including the 50 subjects enrolled in the pilot study.

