9.2.1 Sample Size Re-estimation

After analysis of the pilot study data, the primary endpoint was chosen as the percentage of subjects shedding virus by PCR in NP swab at Day 3.

Assumptions:

- Pooled percentage of subjects with virus detectable by PCR at Day 3 combining both arms is 50% (based on pilot study data)
- Require 90% power to detect difference between arms using two-sided Fisher’s Exact Test with Type I error rate of 0.05.
- Proportion of participants with missing qPCR at Day 3 is 10% (due to losses to follow-up, sample handling and laboratory assay problems).

| Magnitude of difference in proportions between arms (proportions in the two randomized arms) | Sample size (combined across both arms) without adjustment for missing values | Sample size (combined across both arms) with adjustment for 10% with missing values & not accounting for the 50 subjects in the pilot study) |
|--|---|--|
| 25% (37.5% vs 62.5%) | 174 | 194 |
| 20% (40% vs 60%) | 280 | 312 |
| 15% (42.5% vs 57.5%) | 490 | 546 |

Table 9: Re-estimated Sample Size Under Different Treatment Effects

This sample size has been chosen to give approximately 90% power to detect an absolute difference of 15% in the proportion of subjects with undetectable virus shedding at Day 3 in NP swabs (e.g., a reduction of 15% from 57.5% in the oseltamivir arm to 42.5% in the placebo

arm). Less than a 15% absolute difference in viral shedding is unlikely to be viewed as clinically meaningful. Therefore, the revised sample size calculations confirm keeping the sample size 560 subjects, including 50 in the pilot study and 510 in the main study.

This power calculation is based on the fact that approximately 50% of subjects in the pilot study had undetectable virus in NP swabs at Day 3 (pooled over randomized arms) and included allowance for 10% of subjects to have unavailable viral shedding results at Day 3. The calculation assumed use of a t-test to compare proportions using a two-sided type I error rate of 0.05.

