9.4 Statistical Analysis

Details of the planned analysis are presented in the Statistical Analysis Plan.

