9.5 Pilot Study (completed)

Due to the lack of reliable data concerning the AUC virologic endpoint, an “external” pilot study was conducted on the first 50 patients randomized to identify a primary endpoint and method of analysis, and to possibly modify the sample size. To ensure no effect on the type I error rate, data from these 50 patients will be excluded from the primary and secondary efficacy analyses but will be used in other analyses of secondary objectives and regression analyses between clinical and virologic endpoints. The study continues to enroll into the main study while the results of the pilot study are being analyzed. The pilot study will not change what data and samples are collected, but rather how the collected data and samples are analyzed.

Data in the pilot study included duplicate samples for both throat and nose locations and for both methods of measuring virus. Duplicate sampling was only done at baseline. Bland-Altman plots, regression, and correlation were used to assess the reproducibility and variability of both methods of counting virions. Additionally, post randomization viral and clinical endpoints were assessed by study arm to examine the distribution and possibly treatment effect of different clinical and virologic endpoints. This analysis was conducted by a statistician who conveyed the results blinded to treatment allocation to the Pilot Study Analysis Group who recommended a method to the protocol team for a final decision. The analyzing statistician was not part of the group making decisions on which endpoint to use in the main study. Further details for analysis of the Pilot Study will be presented in the Statistical Analysis Plan.

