##### 4.1 Analysis Populations

All tables and figures will note the analysis population used:

- Enrolled Population includes all subjects who had a signed informed consent form for screening.
- Intention To Treat (ITT) Population includes all subjects who were randomized and who received at least one dose of study drug (as defined in Section 7.2.1 of the protocol).
- Primary Efficacy Population (PEP) includes subjects in the ITT population with influenza infection confirmed in central laboratory testing. Given the virology needed to analyze the primary endpoint, this is defined as having an influenza virus isolated and typed in the qualitative PCR evaluation at Day 0 from central laboratory testing (or Day -1 if Day 0 not available).
- The population for the primary analysis is defined as the subgroup of the PE Population that excludes the subjects who participated in the pilot study (because efficacy results for those subjects were used in selecting the primary endpoint for the study).

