#### **4.8.2 Secondary Endpoints: Virologic Endpoints [IRCRSLTS] (PEP and ITT)**

Viral shedding will be assessed by quantitative RT-PCR (reported as  $\log_{10}$  RNA copies/mL) with measurements obtained on Days 0, 3, and 7. These measurements will be used to define the following variables:

- a. Figure and associated table showing number (%) of subjects who had values  $<LOD$ ,  $LOD-<LLOQ$ ,  $\geq LLOQ$  at each visit.
- b. Figure and associated table showing number of subjects and minimum, maximum, median, 25% and 75% percentile of the value of viral shedding at each visit (subjects with values  $<LOD$  will be ranked as lower than detectable values in this analysis; minimum and maximum in table only). Comparison of randomized arms at each of Day 3 and Day 7 will be based on the extension of Wilcoxon's test to handle censoring of measurements which are  $<LLOQ$ .
- c. Number (%) of subjects with undetectable viral load at both Day 3 and Day 7; detectable at Day 3 and undetectable at Day 7; detectable at Day 7 (irrespective of whether or not detectable at Day 3). Analysis will be restricted to subjects with measurements at both Day 3 and Day 7. Comparison of percentages of subjects in this table using the Wilcoxon Test.
- d. Above tables/figures/analyses will be repeated for the subset of subjects who had detectable viral load at Day 0.

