#### **4.9 Secondary Endpoints: Clinical Endpoints [DIARY1] (PEP and ITT)**

Many of the clinical endpoints rely on data collected on diary cards completed by the study participants. The subjects are asked to complete these twice a day (at 8AM and 8PM) on Days 0 through 14 and then again on Day 28. Fever is recorded for the preceding 12 hour period at both times each day, and symptoms are recorded at both times for Days 0 to 7 and then once daily on Days 8 to 14. Functional status (based on the Physical Function domain questions from the SF-36) and two questions giving a global assessment of status are completed daily at 8AM.

- a. Duration of clinical symptoms. Duration of clinical symptoms is defined as the time from Day 0 to the first of two successive measurements at which all clinical symptoms are grade 0 (absent) or 1 (mild). A measurement is considered to be the 8AM or 8PM assessment during Days 0 to 7 (so two measurements are obtained per day) and then the daily assessment thereafter. Time will then be calculated in half-days through to Day 7. For the purposes of defining the endpoint, if the subjects' first two assessments on (baseline assessment and first subsequent diary card assessment) satisfy this criterion, then the duration will be set to zero. Missing values will be ignored [this is equivalent to assuming that a missing value would have (a) indicated at least one grade 2+ symptom if the preceding record includes a grade 2+ symptom or if the first Day 0 value is missing; (b) indicated no grade 2+ symptoms if the preceding and succeeding assessments show no grade 2+ symptoms; and (c) indicated a grade 2+ symptom if the preceding assessment shows no grade 2+ symptom and the succeeding value shows a grade 2+ symptom]. Times will be considered as discrete (i.e. based on the schedule of completion of diary cards) and subjects not having two succeeding assessments with only grade 0 or 1 symptoms at any time during follow-up will be censored immediately after Day 14 (the last scheduled measurement time on which an endpoint can occur).
- Kaplan-Meier plot (and associated table) of the percent of subjects without clinical symptoms per the above definition over time, with the median duration of time to alleviation of such symptoms and its 95% confidence interval.
  - P-value comparing randomized arms from the log rank test.

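### SAP 4.8 keeps the 50 pilot subjects in every secondary efficacy analysis, while Protocol 9.5 excludes them to protect the type I error rate

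*SAP*

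**What the plan says.** Protocol 9.5 describes the first 50 randomized subjects as an external pilot, used to identify the primary endpoint and the method of analysis. Its rule for their data is: "To ensure no effect on the type I error rate, data from these 50 patients will be excluded from the primary and secondary efficacy analyses". The same sentence then permits a narrower use: these data "will be used in other analyses of secondary objectives and regression analyses between clinical and virologic endpoints". Protocol 9.2.1 gives the total of 560 as "including 50 in the pilot study and 510 in the main study".

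SAP 4.1 defines a separate population for the primary analysis, which leaves out the pilot "because efficacy results for those subjects were used in selecting the primary endpoint for the study". The other two efficacy populations, the ITT and the Primary Efficacy Population (PEP), keep it. SAP 4.8 plans the primary endpoint both without and with the pilot, and then says of everything else: "All analyses of secondary efficacy endpoints will be undertaken including the 50 subjects enrolled in the pilot study". The headings of SAP 4.8.2 (virologic) and 4.9 (clinical) name only the PEP and the ITT. SAP 4.6 compares mortality and hospitalization between arms in the ITT; both are listed as secondary endpoints in Protocol 3.3.2.

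**The concern.** The two documents name the same subjects and the same class of analyses, and their rules are opposite. An analyst cannot follow both.

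The protocol ties its rule to the type I error rate. Under the SAP that safeguard is not applied to the Wilcoxon-type tests in 4.8.2, the log-rank, Wilcoxon and proportion tests in 4.9, or the arm comparisons in 4.6. No pilot-excluded result is planned for these endpoints, so a reader of the report could not see whether the pilot data matter.

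The SAP's own reason for the primary exclusion, that pilot efficacy results helped to choose the endpoint, carries over most clearly to endpoints built on the same measurement. These are the Day 3 viral load (4.8.2 b) and the combined Day 3/Day 7 detectability categories (4.8.2 c).

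**Working it through.** **1. Can the texts be reconciled?**
- The permission in Protocol 9.5 covers *other* analyses of secondary objectives. It follows the exclusion of secondary efficacy analyses in the same sentence, so it cannot restore them. It fits objectives such as the link between shedding and symptoms, or self-collected swabs.
- Protocol 9.4 says: "Details of the planned analysis are presented in the Statistical Analysis Plan". Supplying details does not extend to reversing an explicit rule stated one section later.
- Protocol 2.2 assesses secondary objective 1 in the PEP and the ITT, and Protocol 9.3 defines both without removing the pilot. The protocol is therefore not fully consistent with itself. Section 9.5 is the more specific text and gives a reason, so the conflict with SAP 4.8 remains.

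**2. The plan's own sample size.** Inputs from Protocol 9.2.1: 42.5% vs 57.5%, two-sided 0.05, 90% power, 10% missing.
- Uncorrected n per arm = [1.96 × √(2 × 0.5 × 0.5) + 1.2816 × √(0.425 × 0.575 + 0.575 × 0.425)]² / 0.15² = 231.4, or 464 in total after rounding up per arm.
- With continuity correction: (231.4/4) × [1 + √(1 + 4/(231.4 × 0.15))]² = 244.6, so 245 per arm and 490 in total, as in Table 9.
- Allowing for 10% missing: 245/0.9 rounds up to 273 per arm, or 546, as in Table 9.

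The conflict does not depend on these figures. They show only that the inputs used below are the plan's.

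**3. Weight of the pilot.** 50/560 = 0.0893, or 8.9%.

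**4. Shift in an estimate.** For a binary endpoint, assume 1:1 allocation and the same shares missing and confirmed in pilot and main study. Then pooled difference − main-study difference = 0.0893 × (pilot difference − main-study difference).
- Pilot 10 points away: 0.0893 × 10 = 0.9 points.
- Pilot 20 points away: 0.0893 × 20 = 1.8 points.

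For scale, the 95% half-width is 1.96 × √(2 × 0.425 × 0.575 / n per arm):
- 510 randomized, n = 510 × 0.9/2 = 229.5: 9.0 points.
- 560 randomized, n = 560 × 0.9/2 = 252: 8.6 points.

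**5. Type I error, illustration only.** The documents give neither the number of candidate endpoints nor the selection rule. A simulation assumed K candidates with no true effect, correlations of 0 to 0.8, and choice of the candidate most favourable to oseltamivir in the pilot. Two-sided error at nominal 0.05:
- chosen endpoint, pilot excluded: about 0.050;
- chosen endpoint, pilot kept: about 0.050 (K = 2), 0.051 to 0.059 (K = 5), 0.054 to 0.067 (K = 10);
- an endpoint not chosen, pilot kept: 0.048 to 0.050.

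A secondary endpoint close to the chosen one would lie nearer the second line, and an unrelated one nearer the third. These figures are not upper bounds: choice by size of difference regardless of direction was not simulated.

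**6. Price of exclusion.** Standard errors grow by √(560/510) = 1.048. At 42.5% vs 57.5% with 10% missing, normal-approximation power is Φ{[0.15√n − 1.96√0.5]/√0.48875}: 0.898 with n = 229.5 and 0.923 with n = 252. The rates are the primary endpoint's design values, so this is a scale and not the power of any planned secondary test.

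**The case against.** The strongest reply is that little is at stake.
- The confirmatory test already excludes the pilot.
- Neither document gives a multiplicity procedure for the secondary endpoints, so no familywise error rate is being controlled there.
- Protocol 9.5 says the pilot results went to the deciding group blinded to allocation, and that the analysing statistician was not part of that group. This limits selection by direction of effect.
- The clinical endpoints in 4.9 are further from the chosen endpoint than the Day 3 items in 4.8.2.

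All of this stands and sets the size of the point. It does not remove the conflict: Protocol 9.5 describes the blinding and still excludes the pilot.

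A second reply is that a reason may be given elsewhere. The SAP's contents list an entry on key updates to version 1.0, and the front pages were not in the text available here. A justification there is possible, so the documents do not show that the inclusion is unjustified. Protocol version 8 would still state the opposite rule.

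A reader might also infer that the population for SAP 4.8.1 c to e is unclear, since c and d repeat the primary analysis yet are labelled for the PEP only. The text does not support this. The 4.8.1 heading names two populations, the label picks one of them, and SAP 4.1 defines it. Repeating the primary analysis most naturally refers to the method.

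**Conclusion.** The contradiction is firm, because it rests on two explicit sentences that no other passage reconciles. Its expected effect is small. A pilot result 10 to 20 points away from the main study would move a pooled difference by 0.9 to 1.8 points, against a half-width of about 9.0. That rests on equal missingness, an equal confirmed share and borrowed rates.

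A reader might infer that the secondary p-values are materially inflated, or that the primary result is compromised. The first cannot be derived from the documents, which do not state how the endpoint was selected. The second is contradicted by SAP 4.1 and 4.8. What does hold is that a stated safeguard is dropped for all secondary efficacy comparisons, with no planned table that would show whether this matters. It should be fixed before unblinding.

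**What to change.** Before unblinding, do one of the following.

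1. Change SAP 4.8 so that between-arm analyses of secondary efficacy endpoints (4.8.2, 4.9, and hospitalization and mortality in 4.6) exclude the pilot, and give the pilot-inclusive results as labelled supplementary tables. Align the population definitions in Protocol 9.3 and SAP 4.1 with that rule.
2. Amend Protocol 9.5 to allow the inclusion, state why, and add pilot-excluded sensitivity tables for the same endpoints.

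Either is cheap. The SAP already runs both versions for the primary endpoint, and in 4.10 b it repeats the self-swab Day 3 comparison without the pilot. Both options need revised wording and repeated tables. Option 1 also widens standard errors in the main secondary tables by about 5%. Other uses of the pilot data that Protocol 9.5 permits can stay as they are.
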